6.3 LOST TO FOLLOW-UP

A subject will be considered lost to follow-up if he or she fails to complete 3 scheduled check-in visits in a row or fails to complete the follow-up visit and is unable to be contacted by the study site staff.

The following actions must be taken if a subject fails to be available for a required study visit:

- The site will attempt to contact the subject and reschedule the missed visit and counsel the subject on the importance of maintaining the assigned visit schedule and ascertain if the subject wishes to and/or should continue in the study.
- Before a subject is deemed lost to follow-up, the investigator or designee will make every effort to regain contact with the subject (where possible, 3 telephone calls and, if necessary, a certified letter to the subject's last known mailing address or local equivalent methods). These contact attempts should be documented in the subject's medical record or study file.
- Should the subject continue to be unreachable, he or she will be considered to have withdrawn from the study with a primary reason of lost to follow-up.

7 STUDY ASSESSMENTS AND PROCEDURES

7.1 STUDY ASSESSMENTS

All study participants will complete 2 in-person study assessments: 1) Enrollment/Baseline Visit and 2) Week 8 Follow-up Visit. During the 8-week meal delivery intervention, participants will also be sent a weekly electronic survey to report adherence with consuming the study meals (the number of study-provided meals consumed by participants [versus others in the household versus thrown out]) and to self-report their last weight measurement.

Enrollment/Baseline Visit: This visit will take place when participants are 5 to 45 weeks post-delivery. Participants will come to the study laboratory and the visit will take approximately 2-2.5 hours. Staff will review the consent form in detail with the potential participant and answer all of their questions. After providing informed consent to participate in the study, the Baseline Visit will continue with the completion of the following:

Weight and height measurements: Participant weight and height will be measured.

Questionnaires: At the Baseline Visit (i.e., Study Visit 1), participants will complete the following questionnaires:

- FORM 01: Food Allergies & Aversions
- FORM 02: Demographics
- Income Supplemental Questions Form

- FORM 03: Pregnancy & Infant History
- FORM 04: Pittsburgh Sleep Quality Index (PSQI)
- FORM 05: Perceived Stress Scale (PSS-10)
- FORM 06: Diet Satisfaction (DSAT-28)
- FORM 07: Self-Efficacy
- FORM 08: Barriers to Healthy Eating
- FORM 09: Infant Feeding
- FORM 10: Edinburgh Postnatal Depression Scale (EPDS)
- FORM 11: Multidimensional Scale of Perceived Social Support (MSPSS)
- FORM 12: Nutrition Security Survey
- Household Food Security Survey
- International Physical Activity Questionnaire

24-hour diet recalls: Participant 24-hour dietary recalls will be collected using the Automated Self-administered 24-hour Dietary Assessment Tool (ASA24). For this, participants will be asked to report everything they had to eat and drink during the previous day (from midnight-to-midnight) including any dietary supplements. The diet recall will take approximately 30-45 minutes. Participants will be given measuring cups and spoons to assist them with estimating portion sizes when completing the diet recall. Participants will also be given the ASA24 Information handout to assist them with completing 2 additional dietary recalls after Study Visit 1. For this, in the 1-2 weeks following Study Visit 1 (e.g., before beginning the meal delivery intervention) participants will be contacted to complete two additional 24-hour dietary recalls. These recalls may be completed by participants using a unique login for the ASA24 system or, if participants struggle to complete recalls or do not have internet or computer/tablet/cellphone access to complete the recalls themselves, a study staff member may complete the 24-hour recall with the participant over the phone using ASA24. The ASA24 Dietary Assessment Tool is a free, web-based tool developed by the National Cancer Institute of the National Institutes of Health for the collection of 24-hour dietary recalls for research. The ASA24 system does NOT collect any identifying data for study participants. Rather, researchers specify a unique numeric identifier for each respondent. Researchers must use a separate system or database outside of the ASA24 system to store participant numeric identifiers.

Intervention Data Collection: All N=11 women who enroll in the study will receive the study meal delivery intervention. At the baseline visit, women who consent to participate in the study will meet with a trained study staff member who will explain the procedures for placing weekly meal orders and show them how to complete weekly online Qualtrics Surveys which will be sent to participants via email. Participants will be given a study scale and instructed to weigh themselves at least once per week and report their weekly weight measurement on the weekly Qualtrics survey. As part of the weekly emailed Qualtrics survey, participants will also be asked to report intervention adherence (e.g., number of study meals they ate versus others versus that they threw away), adverse events (e.g., flatulence, new or worsening gastroesophageal reflux), and satisfaction with the study meals. Staff will complete weekly calls with participants to obtain their meal orders and to complete a brief check-in to see on how they are doing and utilize motivational interviewing techniques to help women who are struggling to comply with the intervention to problem-solve and develop weekly goals. Staff will document the duration and topics discussed during weekly telephone contacts.

Week 8 Follow-up Visit: This visit will take place during the final week for the study meal delivery intervention. Participants will come to the study laboratory and the visit will take approximately 2-2.5 hours. Participants will be asked to complete the following:

Weight measurements: Participant weight will be measured with participants in light clothing and no shoes.

Questionnaires: At the Follow-up Visit, participants will complete the following questionnaires:

- FORM 04: Pittsburgh Sleep Quality Index (PSQI)
- FORM 05: Perceived Stress Scale (PSS-10)
- FORM 06: Diet Satisfaction (DSAT-28)
- FORM 07: Self-Efficacy
- FORM 08: Barriers to Healthy Eating
- FORM 09: Infant Feeding
- FORM 10: Edinburgh Postnatal Depression Scale (EPDS)
- FORM 11: Multidimensional Scale of Perceived Social Support (MSPSS)
- FORM 12: Nutrition Security Survey
- FORM 13: Health & Demographics Update
- FORM 14: Program Satisfaction
- Household Food Security Survey
- International Physical Activity Questionnaire

Semi-structured, one-on-one interview: Participants will complete a semi-structured, one-on-one interview with a member of the research team. These one-on-one interviews (lasting up to 60 minutes) will be conducted using an interview guide. Interviews will be audio-recorded, transcribed verbatim, and the file will be erased after the transcripts have been verified for completeness. The transcription will not have any identifiable data included as participants will use anonymous names or nicknames during the interview sessions. The recording will be stopped at the end of the interview.

24-hour diet recalls (Follow-Up): Participants will be contacted on 3 separate days and asked to complete three 24-hour dietary recalls over the last 2 weeks of the study intervention (e.g., when participants are still receiving the meal delivery intervention) using the same procedures as described for the Baseline Visit. Briefly, the 24-hour recalls will either be completed directly by participants using the ASA24 system or will be completed over the phone with study staff (and study staff will enter participant recall information into ASA24). Participants will be asked to report everything they had to eat and drink during the previous day (from midnight-to-midnight) including any dietary supplements. Each diet recall will take approximately 30-45 minutes. Participants will be sent a copy of the How to Add a Nourish Meal Instructions handout that will instruct them on how to add one of the study-provided meals to a dietary recall in ASA24.

Participant Medical Records: A designated study staff member with appropriate approvals will obtain access to participant medical records for the retrieval of: date at gestational age (weeks at first dating ultrasound, date (which will be used to calculate gestational age (weeks)) and weight measured at the first prenatal visit; maternal weight and date (which will be used to calculate gestational age (weeks)) at their last prenatal care visit; maternal weight (if available) and gestational age at delivery; maternal diagnosis with gestational diabetes or hypertensive disorders of pregnancy and mode of delivery.

7.2 ADVERSE EVENTS AND SERIOUS ADVERSE EVENTS

7.2.1 DEFINITION OF ADVERSE EVENTS (AE)

Adverse event means any untoward medical occurrence associated with the use of an intervention in humans, whether or not considered intervention-related (21 CFR 312.32 (a)).

7.2.2 DEFINITION OF SERIOUS ADVERSE EVENTS (SAE)

An adverse event (AE) is considered “serious” if, in the view of either the investigator or sponsor, it results in any of the following outcomes:

- Death
- A life-threatening adverse event (of note, the term “life-threatening” refers to an event in which the subject was at risk of death at the time of the event, rather than to an event which hypothetically might have caused death if it were more severe)
- inpatient hospitalization or prolongation of existing hospitalization
- a persistent or significant incapacity or substantial disruption of the ability to conduct normal life functions
- or a congenital anomaly/birth defect.

Important medical events that may not result in death, be life-threatening, or require hospitalization may be considered serious when, based upon appropriate medical judgment, they may jeopardize the subject and may require medical or surgical intervention to prevent one of the outcomes listed in this definition. Examples of such medical events include allergic bronchospasm requiring intensive treatment in an emergency room or at home, blood dyscrasias or convulsions that do not result in inpatient hospitalization, or the development of drug dependency or drug abuse.

7.2.3 CLASSIFICATION OF AN ADVERSE EVENT

7.2.3.1 SEVERITY OF EVENT

For adverse events (AEs), the following guidelines will be used to describe severity:

- **Mild** – Events require minimal or no treatment and do not interfere with the subject’s daily activities.
- **Moderate** – Events result in a low level of inconvenience or concern with the therapeutic measures. Moderate events may cause some interference with functioning.
- **Severe** – Events interrupt a subject’s usual daily activity and may require systemic drug therapy or other treatment. Severe events are usually potentially life-threatening or incapacitating. Of note, the term “severe” does not necessarily equate to “serious.”

7.2.3.2 RELATIONSHIP TO STUDY INTERVENTION

All adverse events (AEs) must have their relationship to study intervention assessed by the clinician who examines and evaluates the subject based on temporal relationship and his/her clinical judgment. The degree of certainty about causality will be graded using the categories below. In a clinical trial, the study product must always be suspect.

- **Related** – The AE is known to occur with the study intervention, there is a reasonable possibility that the study intervention caused the AE, or there is a temporal relationship between the study intervention and event. Reasonable possibility means that there is evidence to suggest a causal relationship between the study intervention and the AE.
- **Not Related** – There is not a reasonable possibility that the administration of the study intervention caused the event, there is no temporal relationship between the study intervention and event onset, or an alternate etiology has been established.

7.2.3.3 EXPECTEDNESS

The Principal Investigator will be responsible for determining whether an adverse event (AE) is expected or unexpected. An AE will be considered unexpected if the nature, severity, or frequency of the event is not consistent with the risk information previously described for the study intervention.

7.2.4 TIME PERIOD AND FREQUENCY FOR EVENT ASSESSMENT AND FOLLOW-UP

The occurrence of an adverse event (AE) or serious adverse event (SAE) may come to the attention of study personnel during study visits or via weekly electronic surveys sent to participants during the study intervention which asks participants to report potential AEs.

All AEs including local and systemic reactions not meeting the criteria for SAEs will be captured on the appropriate case report form (CRF). Information to be collected includes event description, time of onset, clinician's assessment of severity, relationship to study product (assessed only by those with the training and authority to make a diagnosis), and time of resolution/stabilization of the event. All AEs occurring while on study must be documented appropriately regardless of relationship. All AEs will be followed to adequate resolution.

Any medical condition that is present at the time that the subject is screened will be considered as baseline and not reported as an AE. However, if the study subject's condition deteriorates at any time during the study, it will be recorded as an AE.

Changes in the severity of an AE will be documented to allow an assessment of the duration of the event at each level of severity to be performed. AEs characterized as intermittent require documentation of onset and duration of each episode.

The Study Coordinator will record all reportable events with start dates occurring any time after informed consent is obtained until 7 (for non-serious AEs) or 30 days (for SAEs) after the last day of study participation. At each study visit, the Study Coordinator will inquire about the occurrence of AE/SAEs since the last visit. Events will be followed for outcome information until resolution or stabilization.

7.2.5 ADVERSE AND SERIOUS ADVERSE EVENT REPORTING

All serious adverse events must be reported to the IRB according to regulatory requirements. The Principal Investigator will immediately report to the sponsor any serious adverse event, whether or not considered study intervention related, including those listed in the protocol or package insert and must include an assessment of whether there is a reasonable possibility that the study intervention caused the event. Study endpoints that are serious adverse events (e.g., all-cause mortality) must be reported in accordance with the protocol unless there is evidence suggesting a causal relationship between the

study intervention and the event (e.g., death from anaphylaxis). In that case, the investigator must immediately report the event to the sponsor.

All serious adverse events (SAEs) will be followed until satisfactory resolution or until the Principal Investigator deems the event to be chronic or the subject is stable. Other supporting documentation of the event may be requested and should be provided as soon as possible.

7.3 UNANTICIPATED PROBLEMS

7.3.1 DEFINITION OF UNANTICIPATED PROBLEMS (UP)

The Office for Human Research Protections (OHRP) considers unanticipated problems involving risks to subjects or others to include, in general, any incident, experience, or outcome that meets all of the following criteria:

- Unexpected in terms of nature, severity, or frequency given (a) the research procedures that are described in the protocol-related documents, such as the Institutional Review Board (IRB)-approved research protocol and informed consent document; and (b) the characteristics of the subject population being studied;
- Related or possibly related to participation in the research (“possibly related” means there is a reasonable possibility that the incident, experience, or outcome may have been caused by the procedures involved in the research); and
- Suggests that the research places subjects or others at a greater risk of harm (including physical, psychological, economic, or social harm) than was previously known or recognized.

7.3.2 UNANTICIPATED PROBLEM REPORTING

The investigator will report unanticipated problems (UPs) to the reviewing Institutional Review Board (IRB). The UP report will include the following information:

- Protocol identifying information: protocol title and number, PI’s name, and the IRB project number;
- A detailed description of the event, incident, experience, or outcome;
- An explanation of the basis for determining that the event, incident, experience, or outcome represents an UP;
- A description of any changes to the protocol or other corrective actions that have been taken or are proposed in response to the UP.

To satisfy the requirement for prompt reporting, UPs will be reported using the following timeline:

- UPs that are serious adverse events (SAEs) will be reported to the IRB within 10 working days of the investigator becoming aware of the event.
- Any other UP will be reported to the IRB within 10 working days of the investigator becoming aware of the problem.

8 STATISTICAL CONSIDERATIONS

8.1 STATISTICAL HYPOTHESES

- Primary Efficacy Endpoint(s): The primary aim of this study is to assess the feasibility of the study meal delivery intervention. Hypothesis 1: We will successfully achieve >80% intervention adherence, defined as consuming at least 80% of received study meals, during the 8-week intervention.
- Secondary Efficacy Endpoint(s): The secondary aim is to characterize the acceptability of the study meal delivery intervention. Hypothesis 2a: We will collect data to characterize study participation rate and achieve <20% attrition. Hypothesis 2b: Participant reported diet satisfaction will show improvements from baseline to follow-up.

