5.1.2 DOSING AND ADMINISTRATION

Participants in the study receive 10 lunch/dinner-style meals per week delivered to their homes free of charge for a total of 8-weeks. Participants will select the 10 meals that they want each week from a weekly rotating menu that includes nutrition and ingredient information to accommodate participants with food aversions or allergies. Participants place meal orders weekly with study staff who will submit orders to the meal delivery partner. If a participant does not place their weekly order, study staff will select meals based on participant preferences and allergies collected at baseline to ensure they receive meals each week. Each week of the intervention, participants will be automatically sent an electronic survey to report the number of study-provided meals consumed by participants (versus others in the household versus thrown out).

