8.2 SAMPLE SIZE DETERMINATION

The goal of this pilot study was to collect preliminary data regarding the feasibility and acceptability of a meal delivery intervention among postpartum women. As this is a feasibility pilot with the primary goal of capturing process data, a formal power calculation was not conducted. Indeed, effect estimates based on small pilot studies are too imprecise and should not be used to inform future trials.⁹⁶ Instead, we followed recommendations from the National Center for Complementary and Integrative Health (NCCIH) that sample sizes for feasibility studies should be based on “practical considerations including participant flow, budgetary constraints, and the number of participants needed to reasonably evaluate feasibility goals.” With these considerations in mind, the present study aimed to recruit a minimum of 10 participants and up to 20 participants based on the available budget. This was a single-group trial with the primary goal being to obtain process data and preliminary data to inform intervention refinements before pursuing funding for subsequent pilot testing.

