8.3 STATISTICAL ANALYSES

8.3.1 GENERAL APPROACH

At each time of measurement, descriptive statistics will be used to summarize demographic characteristics and process measures, including rates of study participant, retention, and intervention adherence. Average values of outcome measures (e.g., diet satisfaction) will be calculated for baseline and follow-up. No formal statistical analyses will be conducted as this was a single group feasibility study that was not designed to be powered to detect statistical significance.

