8.3.3 ANALYSIS OF THE SECONDARY ENDPOINT(S)

For secondary endpoints, study participation rate (percentage of eligible subjects who agreed to participate out of those who were screened) and retention rate (percentage of enrolled participants

who complete follow-up) will be calculated and reported. Visual representation of the flow of participants through the study will be reported through a CONSORT diagram. Change in participant satisfaction with the diet will be reported as the mean total diet satisfaction score, as well as the mean scores on subscales for Cost Factor and Planning & Preparation Factor, at baseline and follow-up will be reported.¹

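### Hypothesis 2b gives no size of improvement and no deciding score, so only the sign of a mean difference in about 11 women can settle it

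*Combined protocol and SAP*

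**What the plan says.** Hypothesis 2b in section 8.1 reads: "Participant reported diet satisfaction will show improvements from baseline to follow-up". It belongs to the secondary aim, the acceptability of the intervention. In the same section, Hypothesis 1 has a cut-off (more than 80% adherence) and so does the attrition part of Hypothesis 2a (less than 20%). Hypothesis 2b has none.

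Section 8.3.3 turns the change in satisfaction into the "mean total diet satisfaction score, as well as the mean scores on subscales for Cost Factor and Planning & Preparation Factor, at baseline and follow-up". That makes three scores at two time points. Nothing says which score decides 2b, or whether one, any or all must rise.

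Section 8.3.1 confines the analysis to averages: "Average values of outcome measures (e.g., diet satisfaction) will be calculated for baseline and follow-up". It adds: "No formal statistical analyses will be conducted as this was a single group feasibility study". Section 8.2 states that "a formal power calculation was not conducted". On numbers, section 7.1 says "All N=11 women who enroll in the study will receive the study meal delivery intervention".

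No other section gives a minimum important difference, a measure of spread or an interval for diet satisfaction.

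**The concern.** A statement listed among the statistical hypotheses will be reported as supported or not. For 2b the plan produces two means per score and nothing that shows how far they could differ by chance. Any claim of improvement must then rest on whether the follow-up mean is higher than the baseline mean. In a group this small that is close to a coin toss when nothing has changed, and a modest true decline can still look like a gain.

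Separate means also do not show the variation in within-woman change, so a reader could not reconstruct the missing uncertainty. In addition, section 8.3.3 does not say whether the baseline mean is restricted to women who also have a follow-up score.

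At stake is one of the two acceptability hypotheses in a pilot that is meant to guide refinement of the intervention before further pilot testing.

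**Working it through.** The plan states no error rate, effect size or SD for 2b, so there is no figure to reproduce. The check asks how the only available criterion behaves.

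**Inputs from the documents.** N = 11 (7.1); attrition target below 20% (8.1); three scores (8.3.3); no test (8.3.1). Losing 2 of 11 is 18.2%, so meeting the attrition target leaves at least 9 women with both measurements.

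**Assumptions.** Mean changes are roughly normal, and effects are expressed in SDs of the within-woman change. The documents give no correlations between the scores, so a range is used.

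**One score, no true change.** P(mean change > 0) = 0.50 at any n when the change is symmetric and continuous. Allowing for ties, with assumed 5-point items and n from 9 to 20, simulation gives 0.48 to 0.50.

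**One score, true worsening of 0.2 SD, n = 11.** P(mean change > 0) = 1 − Φ(0.2 × √11) = 1 − Φ(0.663) = 0.254. A decline of that size would look like an improvement about one time in four.

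**Three scores, no true change.** For three jointly normal mean changes with zero means:

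P(all rise) = 1/8 + [asin r12 + asin r13 + asin r23] / (4π), and by symmetry P(any rises) = 1 − P(all rise).

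| Subscale–subscale r | Subscale–total r | Any of three rises | All three rise |
|---|---|---|---|
| 0 | 0.4 | 0.81 | 0.19 |
| 0.3 | 0.6 | 0.75 | 0.25 |
| 0.5 | 0.7 | 0.71 | 0.29 |
| 0.7 | 0.85 | 0.65 | 0.35 |

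For the third row: 1/8 + (0.524 + 0.775 + 0.775)/12.566 = 0.125 + 0.165 = 0.290, and 1 − 0.290 = 0.710.

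The chance of apparent support with no true change therefore runs from about 0.2 to about 0.8, depending on a rule that the plan does not state. It is 0.50 if the total alone decides.

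**What an interval would show.** The 95% half-width for the mean change, in SDs of the change, is t(0.975, n−1)/√n:

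- n = 11: 2.228/3.317 = 0.67
- n = 9: 2.306/3 = 0.77

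With no true change, the whole interval lies above 0 in 2.5% of trials. At n = 11 (noncentral t) it lies above 0 with probability 0.32 for a true gain of 0.5 SD, 0.67 for 0.8 SD and 0.85 for 1.0 SD. At n = 9 the last two are 0.56 and 0.75.

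**The case against.** The strongest reply is that this is a descriptive pilot and says so. Section 8.2 declines a power calculation because estimates from small pilots are too imprecise, section 8.3.1 declines formal analysis, and no go/no-go decision depends on 2b. That stands, and it limits the weight of the point. It does not remove it: imprecision is a reason to show the uncertainty, and the plan still lists a directional hypothesis without a way to judge it.

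A reader might infer that a rise on any one of the three scores counts as success, and so put the false-support rate at 65–80%. The documents do not support that. They state an expected direction, list the total first and require all three scores to be reported. The 65–80% also rests on assumed correlations, and the equally open reading that all three must rise gives 19–35%.

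A reader might also discount the Cost and Planning & Preparation subscales because free, prepared meals change those domains directly. Yet the aim in 8.1 is acceptability of the meal delivery intervention, and sections 2.2 and 2.3.2 present financial help and less planning and preparation as part of how it works. The subscales fit that rationale.

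Finally, requiring the lower 95% limit to exceed 0 as a pass mark would bring back the significance test that 8.3.1 deliberately declines. An interval can guide the wording without being made a pass mark.

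**Conclusion.** The concern holds as a gap in how 2b is to be judged. With no size, no deciding score and no measure of uncertainty, the sign of a mean difference in about 11 women is all that can settle it. On one score that sign is favourable 50% of the time when nothing has changed. This figure needs only a symmetric change and does not depend on n. The figures for three scores depend on assumed correlations and on an unstated rule, so they show the ambiguity and are not an error rate of the plan.

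It would go too far to say that the secondary aim is left without evidence. Participation and retention are also secondary endpoints, and section 7.1 collects weekly meal satisfaction, a program satisfaction form and interviews, although 8.3.3 sets out no analysis for those three. The point is a worthwhile and inexpensive improvement to a secondary, descriptive hypothesis.

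**What to change.** - In 8.1 and 8.3.3, name the DSAT-28 total as the score on which Hypothesis 2b is judged.
- In 8.3.3, report the mean within-woman change in the total, among women with both measurements, with its 95% confidence interval.
- Word the 2b conclusion by that interval and not by the sign alone. If it includes 0, give the estimate and interval and call the result inconclusive.
- Report the Cost and Planning & Preparation subscales alongside, in the same descriptive way.
- In 8.3.1, clarify that descriptive confidence intervals are allowed. No significance test or pass/fail rule need be added.

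The cost is a few sentences and one main interval (with matching ones for the subscales) from questionnaires already scheduled at both visits, with no added burden on participants. The downside is that small true gains will often be called inconclusive: for a gain of 0.5 SD of the change at n = 11, about 68% of the time (1 − 0.32).
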